3.2.2.4.2 Planning Technique

A 3D conformal or IMRT planning technique must be used. If not using IMRT, field edges and MLC blocking must be conformal to the PTV. The dose distributions must include corrections for tissue density heterogeneities. Regardless of planning technique, the dose prescription criteria specified shall be prioritized.

Table 1C: Radiation Dose Criteria

Name of Structure	Dosimetric Parameter	Per Protocol	Variation Acceptable
PTV	Dmin (%)	\geq 90	\geq 85
	D100% (%)	\geq 95	\geq 85
	Dmax (%)	\leq 130	\leq 150

Replanning: Because melanoma can respond robustly to radiation and treatments will be every 2 weeks it is possible that the tumor volume will be considerably smaller for subsequent fractions. It is recommended that response be assessed after two fractions for bigger tumors or

tumors where decrease in size can considerably impact OARs and toxicity risk. If there has been a decrease of tumor volume by more than 2-fold then a new plan should be considered.

3.2.2.4.3 Patient specific Quality Assurance (QA)

For photon IMRT plans, patient specific QA is highly recommended. QA is performed by delivering the plan onto a phantom and measuring the dose using an ion chamber array or other 2D/3D device. Typically, measured dose distributions will be compared to planned dose distribution using a Gamma criterion of 4% dose difference and 3 mm distance to agreement. The pass rate should be at least 90% measured for the entire plan.

3.2.2.4.4 Daily Treatment Localization/IGRT

Daily image-guided radiation therapy (IGRT) localization is required for all patients. Either a daily orthogonal kV pair, or cone-beam computed tomography CBCT is acceptable. Institutional guidelines should be followed for daily treatment localization and IGRT. IGRT credentialing is not required for this protocol.

3.2.2.4.5 Duration of Radiation Therapy

Duration of therapy will be per treatment schedule as above. Duration will be shortened, and treatment can be ended early if the patient develops:

- Inter-current illness that prevents further administration of treatment
- Unacceptable adverse event(s)
- Participant decides to withdraw from the study, OR
- General or specific changes in the patient's condition render the participant unacceptable for further treatment in the judgment of the principal investigator or medical oncologist.

3.2.3 Concomitant Treatments

3.2.3.1 Premedication prior to APX005M

All subjects should be premedicated 30 ± 5 minutes before the administration of APX005M with a regimen containing:

- Oral H1 antagonist (e.g., loratadine 10 mg)
- Optional oral H2 antagonist (e.g., ranitidine 150–300 mg, cimetidine 300–800 mg, nizatidine 150–300 mg, and famotidine 20–40 mg)
- Oral nonsteroidal anti-inflammatory drug (may comprise ibuprofen 400 mg or equivalent)
- Acetaminophen 650 mg.

Equivalent quantities of IV formulations of these drugs should be completed 10 ± 5 minutes before the administration of APX005M.

3.2.3.2 **Rescue Medications & Supportive Care Guidelines**

Subjects should receive appropriate supportive care measures as deemed necessary by the treating investigator. Suggested supportive care measures for the management of adverse events (AEs) with potential immunologic etiology are outlined below. These treatment guidelines are intended to be applied when the investigator determines the events to be related to the APX005M and should not substitute for dose delays and/or modifications. Additional guidance for management of AEs suspected to be related to APX005M is provided in the APX005M Investigator's Brochure.

If after evaluation the event is determined by the investigator not to be related, the investigator does not need to follow the treatment guidance outlined in this section. For each disorder, attempts should be made to rule out other causes (such as metastatic disease or bacterial/viral infection) which might require additional supportive care.

- **Diarrhea/Colitis**

Subjects should be carefully monitored for signs and symptoms of enterocolitis (such as diarrhea, abdominal pain, blood or mucus in stool, with or without fever) and of bowel perforation (such as peritoneal signs and ileus). All subjects who experience diarrhea/colitis should be advised to drink liberal quantities of clear fluids. If sufficient oral fluid intake is not feasible, fluid and electrolytes should be substituted via IV infusion. For Grade 2 or higher diarrhea, consider GI consultation and endoscopy to confirm or rule out colitis.

- **Grade 1-2:** for subjects developing Grade 1–2 diarrhea loperamide (2 mg every 2 hours) is strongly recommended at the first onset of symptoms. For subjects with persistent diarrhea despite the use of loperamide, or Grade 2 colitis, the use of oral corticosteroids is recommended. Other antidiarrheal agents (e.g. octreotide) may be used if necessary.
- **Grade 3-4:** treat with IV corticosteroids followed by oral corticosteroids until symptoms improve to Grade 1 or less. Add prophylactic antibiotics for opportunistic infections and consider lower endoscopy.

- **Creatinine Elevation Due to Inflammatory Causes**

- **Grade 2-3:** treat with IV or oral corticosteroids until symptoms improve to Grade 1 or less. Consider renal biopsy with nephrology consult.
- **Grade 4:** treat with IV corticosteroids followed by oral corticosteroids until symptoms improve to Grade 1 or less. Consider renal biopsy and consult nephrologist.

- **Pneumonitis**

- **Grade 2:** request pulmonary and infectious disease consults. Treat with IV or oral corticosteroids until symptoms improve to Grade 1 or less. Consider bronchoscopy, lung biopsy and hospitalization.
- **Grade 3-4:** request pulmonary and infectious disease consults. Hospitalize and treat immediately with IV corticosteroids. Administer additional anti-

inflammatory measures, as needed. Consider adding prophylactic antibiotics for opportunistic infections. Consider bronchoscopy and lung biopsy.

- **Liver Function Tests**

- **Grade 2, and Grade 3 transaminase elevation \leq 72 hours:** monitor liver function tests (incl. total bilirubin levels) more frequently until returned to Grade \leq 1.
- **All other Grade 3, and any Grade 4 transaminase elevation:** treat with IV corticosteroids for 24-48 hours followed by oral corticosteroids until symptoms improve to Grade \leq 1. If no improvement in 3–5 days administer additional immunosuppressive measures (e.g. mycophenolate mofetil), as needed. Consider adding prophylactic antibiotics for opportunistic infections. Consult gastroenterologist.

- **Skin Adverse Events**

- **Grade 1-2:** symptomatic treatment (e.g. antihistamines, topical steroids). For persistent (>1 –2 weeks) or recurrent symptoms consider skin biopsy and treatment delay.
- **Grade 3–4:** consider skin biopsy and consult dermatologist. Treat with IV corticosteroids followed by oral corticosteroids until symptoms improve to Grade 1 or less.

- **Infusion Reaction/Cytokine Release Syndrome**

Precautions should be observed during the administration of APX005M. Emergency treatment including oxygen, oral and endotracheal airways, intubation equipment epinephrine, antihistamines, and corticosteroids should be available and used as medically required and at the Investigator's discretion.

- **Grade 2:** stop infusion and treat symptoms following guidance in Table 2. If symptoms resolve within two hours, the infusion may be restarted at 50% of the original infusion rate (e.g., from 100 mL/hr to 50 mL/hr).
- **Grade 3–4:** stop infusion and treat symptoms following guidance in Table 2.

Subjects should be instructed that symptoms associated with cytokine release syndrome/infusion reaction may occur within 48 hours following the administration of APX005M and if such symptoms develop while they are at home, they should contact the Investigator and/or seek emergency medical care if necessary.

Table 2: Guidance for Management of Cytokine Release/Infusion Reaction Symptoms

Suspected Cytokine Release/Infusion-related Toxicity	Recommended Treatment				

 Mild toxicity requiring symptomatic treatment only (e.g., fever, nausea, fatigue, headache, myalgia, malaise) 	
 Vigilant supportive care Maintain adequate hydration Antipyretics, non-steroidal anti-inflammatory drugs, antihistaminics, anti-emetics, analgesics as needed In case of mild symptoms persisting for >24 hours assess for infections; empiric treatment of concurrent bacterial infections 				

 Symptoms or clinical findings requiring and responding to moderate intervention, such as: 
 O₂ requirement <40% Hypotension responsive to fluids ± low dose of one vasopressor (e.g., <50 mg/min phenylephrine) CTCAE Grade 2 organ toxicity 	
 
  
 No extensive co-morbidities 	 
 All of the above Monitor cardiac and other organ functions closely 	
 
  
 Extensive co-morbidities Age ≥70 years 	 
 All of the above Administer tocilizumab first Administer corticosteroids if symptoms worsen or do not improve in <4 hours 	
 
	
 No extensive co-morbidities 	
 All of the above Monitor cardiac and other organ functions closely 	
 Extensive co-morbidities Age ≥70 years 	
 All of the above Administer tocilizumab first Administer corticosteroids if symptoms worsen or do not improve in <4 hours

 No extensive co-morbidities 	
 All of the above Monitor cardiac and other organ functions closely 				

 Extensive co-morbidities Age ≥70 years 	
 All of the above Administer tocilizumab first Administer corticosteroids if symptoms worsen or do not improve in <4 hours 				

 Symptoms or clinical findings requiring aggressive intervention, such as: 
 O₂ requirement ≥40% Hypotension requiring high dose or multiple vasopressors Ventilator support required CTCAE Grade ≥3 organ toxicity 					

- Any Other Possibly Immune Mediated Toxicity**
 - Grade 2:** symptomatic treatment per local guidelines
 - Grade 3–4:** Consult Apexigen Medical Monitor (or designee). Administer IV corticosteroids followed by oral corticosteroids until symptoms improve to Grade 2 or less. Consider adding prophylactic antibiotics for opportunistic infections. If symptoms worsen or for atypical presentation consider and additional immunosuppressive measures per local guidelines.

3.2.3.3 Permitted Concomitant Medications

All treatments that the investigator considers necessary for a subject's welfare may be administered at the discretion of the investigator in keeping with the community standards of medical care. All concomitant medication received from the time of first dose of APX005M and up to 30 days after the last dose will be recorded on the electronic case report form (eCRF) including all prescription, over-the-counter, herbal supplements and IV medications and fluids.

3.2.3.4 Prohibited and/or Restricted Therapies

Subjects are prohibited from receiving the following therapies during the Screening Period and Treatment Period of this trial:

- Antineoplastic systemic chemotherapy or biological therapy
- Investigational agents other than APX005M
- Radiation therapy not specified in this protocol (radiation therapy to a symptomatic solitary lesion or to the brain may be considered on a case-by-case basis after consultation with Apexigen Medical Monitor [or designee]). The subject must have clear measurable disease outside the radiated field.
- Live vaccines within 30 days prior to the first dose of trial treatment and while participating in the trial. Examples of live vaccines include, but are not limited to, the following: measles, mumps, rubella, chicken pox, yellow fever, rabies, BCG, intranasal influenza vaccines and typhoid (oral) vaccine. Seasonal influenza vaccines for injection and COVID-19 vaccines are allowed as long as they can be administered 6–7 days after last dose of APX005M.
- Systemic corticosteroids for any purpose other than to modulate symptoms from an event of clinical interest of suspected immunologic etiology. The use of physiologic doses of corticosteroids may be approved after consultation with the Apexigen Medical Monitor (or designee). Inhaled corticosteroids are allowed for management of asthma.
- Medications described in the Exclusion Criteria.

Subjects who, in the assessment by the investigator, require the use of any of the aforementioned treatments for clinical management will be discontinued from study treatment.

Herbal medicine for anticancer treatment (such as botanical formulation 'Xiao Chai Hu Tang') should be stopped 1 week prior to first dose of APX005M. Subjects taking narrow therapeutic index medications (such as warfarin, phenytoin, quinidine, carbamazepine, phenobarbital, cyclosporine, and digoxin) should be monitored proactively.

There are no prohibited therapies during the Follow-up Period.

3.2.4 Retreatment Criteria

Subjects that do not meet any of the criteria for treatment discontinuation may start a new cycle of APX005M ± SBRT as scheduled if $\text{WBC} \geq 2,000/\text{mm}^3$, $\text{ANC} \geq 1,000/\text{mm}^3$, platelets $\geq 100,000/\text{mm}^3$, and suspected adverse reactions have resolved to baseline or Grade ≤ 1 (excluding Grade 2 alopecia and Grade 2 fatigue). Subjects who have experienced a Grade ≤ 2 skin suspected adverse reaction may resume treatment in the presence of Grade 2 skin toxicity.

If a subject fails to meet criteria for retreatment then the treatment cycle should be delayed and the subject should be re-evaluated weekly.

3.2.5 Dose Modifications

Management of suspected adverse drug reactions may require reduction of the APX005M dose or interruptions of the radiotherapy. If a subject experiences several toxicities, the recommended dose adjustment should be based on the highest grade toxicity. All dose reductions for APX005M, if required, will follow the instructions described in Table 3.

Table 3: Dose Modifications for Toxicity

	Action Taken with APX005M			Action Taken with SBRT
	1 st Occurrence	2 nd Occurrence	3 rd Occurrence	
Hematologic Toxicity				
Neutrophils (ANC) $<500/\text{mm}^3$ Lasting ≥ 5 days	Reduce to 0.2 mg/kg	Reduce to 0.1 mg/kg	Discontinue	Defer to radiation oncologist*
Neutropenic Fever (Body Temperature $\geq 38.5^\circ\text{C}$ (oral) and ANC $<1000/\text{mm}^3$)	Reduce to 0.2 mg/kg	Reduce to 0.1 mg/kg	Discontinue	Defer to radiation oncologist*
Platelets $<25,000/\text{mm}^3$	Reduce to 0.2 mg/kg	Reduce to 0.1 mg/kg	Discontinue	Defer to radiation oncologist*
Platelets $<50,000/\text{mm}^3$ with Significant Bleeding or Requiring Blood Transfusion	Reduce to 0.2 mg/kg	Reduce to 0.1 mg/kg	Discontinue	Defer to radiation oncologist*
Non-hematologic Toxicities				
Nausea/Vomiting \geq Grade 3 Despite Optimal Medical Treatment	Reduce to 0.2 mg/kg	Reduce to 0.1 mg/kg	Discontinue	Hold treatment until symptoms improve to Grade ≤ 1
Diarrhea \geq Grade 3 Despite Optimal Medical Treatment	Reduce to 0.2 mg/kg	Reduce to 0.1 mg/kg	Discontinue	Hold treatment until symptoms improve to Grade ≤ 1
CRS Grade 3 ≤ 7 days	Reduce to 0.2 mg/kg	Reduce to 0.1 mg/kg	Discontinue	Defer to radiation oncologist*
CRS Grade 3 >7 days	Discontinue	-	-	Discontinue
CRS Grade 4	Discontinue	-	-	Discontinue
Increased Bilirubin Grade ≥ 3	Discontinue	-	-	Discontinue

	Action Taken with APX005M			Action Taken with SBRT
	1 st Occurrence	2 nd Occurrence	3 rd Occurrence	
Increased AST, ALT Grade 3	Reduce to 0.2 mg/kg [#]	Reduce to 0.1 mg/kg [#]	Discontinue	Hold treatment until Grade \leq 1
Increased AST, ALT Grade 4	Discontinue	-	-	Discontinue
Pneumonitis Grade 2	Reduce to 0.2 mg/kg	Reduce to 0.1 mg/kg	Discontinue	Hold treatment until Grade \leq 1. Discontinue on 2 nd occurrence
Pneumonitis Grade \geq 3	Discontinue	-	-	Discontinue
Esophagitis Grade 2	Reduce to 0.2 mg/kg	Reduce to 0.1 mg/kg	Discontinue	Hold treatment until Grade \leq 1
Esophagitis Grade \geq 3	Discontinue	-	-	Discontinue
Gastric or Small Bowel Ulcer Grade \geq 2	Reduce to 0.2 mg/kg	Reduce to 0.1 mg/kg	Discontinue	Discontinue
Colitis or Proctitis Grade \geq 3	Discontinue	-	-	Discontinue
Other \geq 3 Grade Toxicities (except Alopecia) [§]	Adjusted as medically indicated after discussion with Sponsor			Defer to radiation oncologist*

Abbreviations: CRS = cytokine release syndrome

For all toxicity \leq Grade 2, the current dose should be maintained

* Investigator will defer to the radiation oncologist as to whether an interruption of the radiation therapy is also indicated.

For subjects with liver metastasis reduce dose only if Grade 3 $>$ 72 hours

[§] In the event of the “other” Grade 3 or 4 non-hematologic toxicities that, in the opinion of the Investigator, are unrelated to the investigational therapy, subject may continue on therapy with or without dose reduction only after documented discussion with the Apexigen Medical Monitor (or designee).

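### Protocol Table 3 gives opposite APX005M instructions for three Grade 2 toxicities, and no text says which one governs

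*Protocol*

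**What the plan says.** Protocol Section 3.2.5 makes the table binding: "All dose reductions for APX005M, if required, will follow the instructions described in Table 3".

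- **The footnote** states that for all toxicity at or below "Grade 2, the current dose should be maintained". It lists no exceptions and is not tied to particular rows.
- **Three rows** require APX005M action at Grade 2: "Pneumonitis Grade 2", "Esophagitis Grade 2", and "Gastric or Small Bowel Ulcer Grade" 2 or higher. All three give the same schedule: reduce to 0.2 mg/kg, then to 0.1 mg/kg, then discontinue.

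The other places where a reader might look for a tie-break are these:

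- **Protocol 3.2.3.2 (supportive care)** tells sites how to treat Grade 2 pneumonitis: "request pulmonary and infectious disease consults. Treat with IV or oral corticosteroids until symptoms improve to Grade 1 or less". It says this guidance "should not substitute for dose delays and/or modifications", and it refers to the Investigator's Brochure, which is not among the documents reviewed.
- **Protocol 3.2.4 (retreatment)** allows a new cycle once "suspected adverse reactions have resolved to baseline or Grade" 1 or lower, with listed exceptions. It sets the timing of the next dose, not its level.
- **Protocol 3.2.6.1 and SAP 2.3.3 (discontinuation)** send toxicity-related stopping back to the dose modification guidelines.
- **SAP 4.5.1.6** describes delays and reductions as recorded in the database and does not interpret Table 3.

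**The concern.** Both instructions sit in the table that sites are told to follow, and they cannot both be obeyed for a Grade 2 event in one of the three rows. The footnote covers all toxicity of Grade 2 or lower. It is not limited to toxicities the table leaves unlisted.

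The stake is patient safety. Under the footnote, a subject who recovers from Grade 2 pneumonitis, esophagitis or an ulcer resumes APX005M at full dose, and the automatic stop at the third occurrence disappears. These events are foreseeable in Cohort 3: Protocol Tables 1A and 1B name esophagitis, gastric and duodenal ulceration, and pneumonitis as organ endpoints for the radiation constraints (at Grade 3 or higher), so the three rows look deliberate.

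The literal footnote also fits badly with the SBRT column, which is not itself in conflict. A Grade 2 ulcer, or a second Grade 2 pneumonitis, ends SBRT permanently, yet APX005M would continue unchanged.

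**Working it through.** **Step 1. Count the rows in conflict.** Table 3 has 4 hematologic and 15 non-hematologic rows, 4 + 15 = 19.

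- The hematologic triggers are ANC <500/mm³, ANC <1000/mm³ with fever, platelets <25,000/mm³, and platelets <50,000/mm³ with bleeding or transfusion. By the grading in SAP Table 8 all are Grade 3 or 4 counts, so the footnote does not reach them.
- Of the 15 non-hematologic rows, 12 start at Grade 3 or 4 and 3 include Grade 2.
- In conflict: 3. Not in conflict: 4 + 12 = 16.

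**Step 2. Look for a precedence rule.** The only priority rule in Protocol 3.2.5 is to act on the highest grade when a subject has several toxicities. It does not settle row against footnote for a single Grade 2 event. The sections listed above do not settle it either.

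**Step 3. Size the difference.** Inputs: starting dose 0.3 mg/kg (SAP 4.5.1.2); reduced doses 0.2 and 0.1 mg/kg (Table 3); cycles of 3 weeks in Cohort 1 and 2 weeks in Cohorts 2 and 3 (Protocol 2.2). The comparison assumes a subject at 0.3 mg/kg whose site applies the footnote each time.

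| Occurrence | Footnote | Row | Ratio |
|---|---|---|---|
| 1st | 0.3 mg/kg | 0.2 mg/kg | 0.3/0.2 = 1.5 |
| 2nd | 0.3 mg/kg | 0.1 mg/kg | 0.3/0.1 = 3.0 |
| 3rd | 0.3 mg/kg | discontinue | – |

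Planned dose intensity after the event (dose divided by cycle length, in the mg/kg per week unit of SAP 4.5.1.3):

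| | Footnote | Row, after 1st | Row, after 2nd |
|---|---|---|---|
| Cohort 1 | 0.3/3 = 0.100 | 0.2/3 = 0.067 | 0.1/3 = 0.033 |
| Cohorts 2 and 3 | 0.3/2 = 0.150 | 0.2/2 = 0.100 | 0.1/2 = 0.050 |

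Relative dose intensity of those cycles (SAP 4.5.1.4), taking the starting regimen as the target: 0.3/0.3 = 100% under the footnote; 0.2/0.3 = 66.7%, then 0.1/0.3 = 33.3%, under the rows. These figures assume no delay. Waiting for recovery under Protocol 3.2.4 lowers intensity under either reading, so they are upper bounds.

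**Step 4. Trace to the outputs.** SAP 5.3.3.1.1 counts subjects with dose reductions, and SAP 5.3.3.2.1 counts subjects with a TEAE leading to reduction or discontinuation. With planned cohorts of 11, 11 and 18, one subject handled differently moves a cohort percentage by 1/11 = 9.1 or 1/18 = 5.6 points.

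**The case against.** The strongest reply is that the table's structure shows the intent. Grade 2 pneumonitis and Grade 2 esophagitis have their own rows, separate from Grade 3 and above, each with a three-step APX005M schedule. Read literally, the footnote would leave those APX005M cells with no function. Read as a rule for unlisted toxicities, it complements the catch-all row for other events of Grade 3 or higher, and it supplies a dose where Protocol 3.2.4 allows treatment to go on with Grade 2 fatigue, alopecia or skin toxicity. This is persuasive about intent. It does not put a precedence rule into the document, and a site should not have to infer one to choose between full dose, reduced dose and stopping.

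Second, the route to harm is narrow, and this stands. Redosing waits for recovery, Grade 2 pneumonitis prompts consults and corticosteroids, and Protocol 3.2.6.1 still requires stopping on the investigator's opinion, for failed steroid taper, or for failure to recover (with an exception the Medical Monitor may approve). SAP 5.3.5 describes roughly monthly medical monitoring meetings and a safety committee about every three months. The threefold difference needs a second episode in the same subject, and the missed stop needs a third.

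Third, the exposure and TEAE tables report what was given and recorded, so they are accurate under either reading. This also stands: what is lost is consistency of meaning between sites. The Per Protocol criteria in SAP 3.3.4 do not list dose-modification deviations, so that population would not change under the stated criteria.

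**Conclusion.** The contradiction is real and should be fixed. Three of the 19 Table 3 rows conflict with the footnote; for the ulcer row the conflict is limited to Grade 2. From the starting dose, the footnote gives 1.5 times and then 3 times the dose the rows order, and it removes the stop at the third occurrence. This is a matter of patient safety and consistent conduct. It does not affect sample size, the response-rate estimate or its confidence interval.

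The size rests on the subject being at 0.3 mg/kg and the site applying the footnote literally. The documents give no frequency for these events, so no number of affected subjects can be stated. The Investigator's Brochure and the Deviation Plan were not available and might bear on practice, but nothing in the protocol or SAP sets the order of precedence.

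**What to change.** Reword the footnote to: *For all toxicity ≤ Grade 2, the current dose should be maintained unless otherwise specified in Table 3.* The specific and safer rows then govern.

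If any subject is still being dosed, send sites a short clarification. The last subject was enrolled on 21-Oct-2021 (SAP 5.3.8) and APX005M is given for up to 12 months (Protocol 3.2.1). If dosing began soon after enrolment, the letter is useful only until about late October 2022. The documents do not show whether anyone remains on treatment.

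Before database lock, apply the same reading when dosing deviations are classified, consistent with the approved Deviation Plan (SAP 5.2.1). Where a site followed the footnote as written, record that, so an ambiguous instruction is not reported as plain non-compliance.

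The cost is one added phrase and at most one letter. Sample size and visit schedule do not change.
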